#### Costs to participants

No charges will be made to any participants or parental guardians.

#### Payment for Participation

Participants will be given a \$50- \$100 Amazon gift card for each session of the study in which they participate, given at the time of the visit. We will start by offering a \$50 gift

# CIONIC

card, but if we struggle to recruit will apply for a revision to increase the compensation up to \$100.

# Statistical Analysis Plan

In this analysis, we plan to investigate whether the impact of FES on gait is statistically significant relative to unstimulated gait by pairwise comparison (single sample, pre-test post-test).

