### Task 3: Treadmill trial

- Participant will be guided onto a treadmill with side handles.
- An overhead safety harness will be fitted to the participant.
- Walking will be initiated on the treadmill at a rate no more than the participant's comfort level at a participant-reported speed for up to 5 minutes while movement data is collected.

Data will be reviewed to confirm readiness for treadmill gait protocol.

- The process will then be repeated up to 5 times for walking intervals of up to 2 minutes while data is collected and reviewed.
- Verbal check-in with participant for pain, understanding and need for a break.

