## Task 4: Treadmill trial with stimulation assist

- Participant remains on the treadmill with side handles.
- An overhead safety harness remains fitted to the participant.
- A gait assist algorithm will be entered into the Apollo system.
- Walking will be initiated on the treadmill at a rate no more than the participant's comfort level
- After notifying participant, the electrical stimulation algorithm will be applied to the leg electrodes, starting at 0mA and slowly increased until effective gait is achieved or the participant reports discomfort. If pain or discomfort is reported the stimulation and treadmill will be stopped immediately.
- The process may be repeated up to 10 times with different gait assist algorithms.
- Verbal check-in with participant for pain, understanding and need for a break.

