## Power Analysis

An *a priori* power analysis was used to determine that we require eighteen or more participants to achieve 80% power to reject the null hypothesis, which states there is no difference between pre-test (noFES) and post-test (FES) conditions in a pairwise comparison with a significance level (alpha) of 0.05. An effect size of 0.7 was used for the power analysis based on a previous study of FES impact on post-stroke participants.

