## Reported Outcomes

For each metric of interest, we will take the average of each participant's metric values across steps for both noFES and FES walking. We will also report the 95% confidence interval for the differences between FES and noFES outcome metrics.

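### Session C always measures the unstimulated treadmill block before FES walking, so the SAP's pre-post test cannot separate FES from time on the treadmill

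*SAP*

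**What the plan says.** The opening section of the SAP sets one inferential question: "whether the impact of FES on gait is statistically significant relative to unstimulated gait by pairwise comparison (single sample, pre-test post-test"). Its Power Analysis section fixes the order in the null hypothesis, namely that "there is no difference between pre-test (noFES) and post-test (FES) conditions in a pairwise comparison". For the data, Reported Outcomes says "we will take the average of each participant's metric values across steps for both noFES and FES walking". The test is a paired t-test, or a Wilcoxon signed rank test if normality fails, at 0.0125 for each of four metrics.

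In the protocol, Session C is the only session with stimulated walking. Task 3 is unstimulated treadmill walking for up to 5 minutes. A check follows: "Data will be reviewed to confirm readiness for treadmill gait protocol". Then: "The process will then be repeated up to 5 times for walking intervals of up to 2 minutes while data is collected and reviewed". Task 4 comes next: "Participant remains on the treadmill with side handles". Walking starts, the participant is notified, and stimulation is applied "starting at 0mA and slowly increased until effective gait is achieved or the participant reports discomfort". "The process may be repeated up to 10 times with different gait assist algorithms". In both tasks the treadmill speed is limited by comfort; neither task requires it to match the other.

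**The concern.** Every participant gives the designated noFES block first and the FES block second, on the same treadmill in the same visit. Condition and time are therefore tied together. Any change that comes with time (warming up, getting used to the treadmill, tiring) enters the FES-minus-noFES difference along with whatever FES does. A different self-chosen speed in Task 4 would enter it too.

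The SAP treats a significant difference as the impact of FES. Followed as written, part of a significant result could come from time on the treadmill, and fatigue could equally hide a real benefit.

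The SAP also does not say which Task 3 walking supplies the noFES average. Nor does it say whether Task 4 steps before or during the rise from 0 mA, or under every algorithm tried, count as FES.

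**Working it through.** **1. Order and duration.** Task 3 allows 5 + 5 × 2 = 15 minutes of unstimulated walking, all before Task 4. Neither document provides a control group, a reversed order, a designated noFES block after FES, or a time term.

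**2. What the test estimates.** Write τ for the FES effect and δ for everything else that differs between the later and earlier walking (drift, speed). The mean paired difference has expectation τ + δ. The design gives one mean for two unknowns, so the data cannot divide it.

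**3. Lead-ins.** Each Task 4 run starts with walking before stimulation is applied, so some unstimulated steps can follow earlier FES runs. Their length is not specified, the SAP does not designate them as noFES, and carry-over from the previous run is possible. They do not separate τ from δ as the plan stands.

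**4. The plan's own figure.** For a two-sided paired t-test (sidedness is not stated; two-sided assumed), power comes from the noncentral t with n − 1 df and noncentrality d√n. With d = 0.7, n = 18 and alpha 0.05, the noncentrality is 0.7 × √18 = 2.97, the critical value is 2.110 and power is 79.9%. The SAP's 18 participants for 80% reproduces within rounding.

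**5. Illustration with τ = 0.** The same formula, with an assumed δ in SDs of the paired difference and alpha 0.0125 (critical value 2.793 at n = 18 and 2.759 at n = 20). Table 1 of the protocol gives about 10 + 10 = 20 participants for Session C.

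| Assumed δ | Noncentrality, n = 18 | Rejects | Noncentrality, n = 20 | Rejects |
|---|---|---|---|---|
| 0 | 0 | 1.25% | 0 | 1.25% |
| 0.2 | 0.85 | 4.3% | 0.89 | 4.8% |
| 0.3 | 1.27 | 9.1% | 1.34 | 10.3% |
| 0.5 | 2.12 | 28.5% | 2.24 | 32.9% |

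The documents give no drift size; every δ here is an assumption.

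**6. What the remedies leave.** Assume full-length intervals, F = 10 to 20 minutes of Task 4 walking, and all of it averaged.

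- As planned, under linear drift, the block centres are at 7.5 and 15 + F/2 minutes, a gap of 12.5 (F = 10) or 17.5 (F = 20).
- Last 4 minutes of Task 3 as baseline, order unchanged: centre 13, gap 7 or 12, which is 7/12.5 = 56% or 12/17.5 = 69% of the as-planned bias.
- Two intervals moved after Task 4, FES compared with the average of a pre block (minutes 7 to 11) and the post block: centres 9 and 13 + F, average 11 + F/2, equal to the FES centre, so 0%. If only the last 4 minutes of Task 4 counted as FES, 24% to 46% would remain.

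For learning that levels off with a 3-minute constant, the late Task 3 baseline leaves 6–7% and the averaged blocks 10–12%. With 10- to 20-minute constants the late baseline leaves 35–55%, while the averaged blocks leave 7–19% over all constants from 3 to 20 minutes. For a quadratic drift that rises and then falls (peak at 16 minutes, F = 10), the averaged blocks keep 63% and the late baseline 21% in size; with the peak at 21 minutes and F = 20, 74% and 11%. Other peaks reverse that ranking. Neither option is better throughout.

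**7. Precision of a before-versus-after noFES check.** The 95% CI half-width is t/√n: 2.110/√18 = 0.50 SD of that difference at n = 18, and 2.093/√20 = 0.47 at n = 20. A non-significant check would not exclude a drift of 0.3 SD.

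**The case against.** The strongest reply is that the SAP openly calls this a single-sample pre-post comparison, and that the study collects data for device development. The protocol's Statistical Analysis section says it is not meant to yield statistically significant data for a diagnosis or recommendation. That stands and lowers the stakes. It does not settle the matter: the SAP adds a Bonferroni-corrected test of the impact of FES, and the protocol allows aggregate data to go to the FDA in support of submissions.

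A second reply is that some unstimulated walking must come first, because Task 3 data are reviewed for readiness, and that up to 15 minutes may use up most of the learning. Both are fair. But the SAP does not exclude early walking from the noFES average, and fatigue remains possible.

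A third reply is that the Task 4 lead-ins give later noFES steps. A reader might infer from the task order that every unstimulated step precedes FES; that is too strong, for the reason in step 3. A within-run contrast using these steps might help to track drift, but with unspecified length and possible carry-over it cannot be relied on.

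A reader might also infer that self-managed speed guards against order effects. The documents do not support this: without a matching requirement, speed may itself differ between conditions.

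Finally, the undefined noFES and FES steps would be a gap under any order. That is true, but the definition decides how much drift enters the comparison, so it belongs in the same fix.

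**Conclusion.** The concern holds as a limit on attribution. With a fixed order and no control, designated later noFES block or time term, the paired test cannot tell an FES effect from the effect of time on the treadmill or a change of speed. This follows from the documents and needs no numerical assumption.

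A reader might go further and infer that the result is biased towards FES, or that the false-positive rate is some stated figure. The documents support neither. Warm-up and learning could favour FES, fatigue could work against it, and the net size is unknown; the rejection rates above show only what assumed drifts would do.

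A reader might also infer that reordering, with both comparisons significant, would justify crediting FES. It would not: some learning-then-fatigue patterns push both comparisons the same way, and speed could still differ. The matter deserves correction in the SAP, at limited stakes given the protocol's stated purpose.

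**What to change.** **In the SAP:**

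1. Take the late Task 3 intervals (for example, the last two completed) as the noFES baseline and treat earlier walking as familiarisation. State which Task 4 steps and runs count as FES, excluding the lead-in and ramp steps.
2. Report walking speed in each condition.
3. Describe the result as a before-after change during FES walking, not as the effect of FES alone.

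This costs a few sentences and fewer noFES steps in the baseline.

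**Optional, by short protocol amendment:** keep the initial walk and readiness review first, and carry out two of the already planned 2-minute unstimulated intervals after Task 4. The maximum stays at 15 minutes: 5 + 3 × 2 = 11 before and 2 × 2 = 4 after. Report the before-versus-after noFES difference with its CI as a combined drift and carry-over check, not as pass or fail. Report FES against the average of the pre and post blocks as a sensitivity analysis. Do not make joint significance a rule for attribution, and do not claim that averaging removes drift: that needs linear drift, full-length intervals and counted FES steps centred in Task 4.

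No participants or equipment are added. The downsides are possible carry-over into the post block and slightly more walking for those who would have done fewer repeats, which matters for children given the protocol's aim of under 1.5 hours.

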## Power Analysis

An *a priori* power analysis was used to determine that we require eighteen or more participants to achieve 80% power to reject the null hypothesis, which states there is no difference between pre-test (noFES) and post-test (FES) conditions in a pairwise comparison with a significance level (alpha) of 0.05. An effect size of 0.7 was used for the power analysis based on a previous study of FES impact on post-stroke participants.

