**Table 1. Summary of protocol session**

	Session A	Session B	Session C
Specific Aim	Movement measurement	Muscle activation & usability	FES for Gait Assistance
Involves data collection?	Yes	Yes	Yes
Involves stimulation?	No	Yes	Yes
Approximate # of adult participants	20	20	10
Approximate # of pediatric participants	10	10	10
Activity	Measure movement during walking without any intervention.	Measure muscle activity and effect of FES on muscles only (no movement).	Measure effect of FES on gait.

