## Tests of Statistical Significance

The Shapiro-Wilk test for normality will be used to assess the assumption of normality. If the outcome variable is approximately normally distributed, a paired t-test will be used to statistically compare noFES and FES outcome metrics. If the normality assumption is not met, the Wilcoxon signed rank test will be used as an alternative to the paired t-test for this statistical comparison. Bonferroni multiple hypothesis correction will be utilized (four outcome metrics), and our corrected significance level for comparison is 0.0125 (0.05 divided by the four hypotheses tested).

 N. Kapadia, B. Moineau, and M. R. Popovic, "Functional Electrical Stimulation Therapy for Retraining Reaching and Grasping After Spinal Cord Injury and Stroke," *Front. Neurosci.*, vol. 14, p. 718, Jul. 2020, doi: 10.3389/fnins.2020.00718.

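### The SAP computes power at alpha 0.05 but judges every test at 0.0125, so 18 participants give about 58% power per metric, not 80%

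*SAP*

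**What the plan says.** The SAP's Power Analysis states that "we require eighteen or more participants to achieve 80% power to reject the null hypothesis", and that this applies "in a pairwise comparison with a significance level (alpha) of 0.05". On the effect size it says: "An effect size of 0.7 was used for the power analysis based on a previous study of FES impact on post-stroke participants".

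The SAP's Tests of Statistical Significance section says "Bonferroni multiple hypothesis correction will be utilized (four outcome metrics"), and that "our corrected significance level for comparison is 0.0125 (0.05 divided by the four hypotheses tested"). Each metric is compared by a paired t-test, or by a Wilcoxon signed rank test if normality fails. No metric is singled out as primary, and none is left uncorrected. The Power Analysis does not mention the correction.

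Footnote 1 of the SAP gives the source of the effect size. The title printed there is "Functional Electrical Stimulation Therapy for Retraining Reaching and Grasping After Spinal Cord Injury and Stroke".

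The SAP gives no target above eighteen. In the protocol, Table 1 plans about 10 adults for Session C (FES and gait), and its row "Approximate # of pediatric participants" gives 10 for the same session, so about 20 in all.

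**The concern.** Power is a property of a test at a given threshold. The SAP computes it at one threshold and decides at another that is four times stricter. A reader who relies on the 80% would take a non-significant metric as fairly strong evidence that FES does not change it. At the threshold actually used, that reading is not justified.

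The effect size adds to the problem. The SAP compares walking with and without stimulation, while the cited title is about retraining the upper limb. Nothing in the documents shows how 0.7 was derived or why it should apply to gait. Power at 0.0125 falls quickly if the true effect is smaller.

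**Working it through.** **Inputs**
- Effect size 0.7, power 80%, n = 18, alpha 0.05: SAP, Power Analysis.
- Four metrics, threshold 0.05 / 4 = 0.0125: SAP, Tests of Statistical Significance.
- Session C enrolment of about 10 + 10 = 20: protocol, Table 1.
- Assumptions, because the SAP does not state them: the test is two-sided, and 0.7 is the mean paired difference divided by the standard deviation of the paired differences.

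**Formula.** For a paired t-test with n participants, the statistic follows a noncentral t distribution with n − 1 degrees of freedom and noncentrality d × √n. Power is the probability that its absolute value exceeds the two-sided critical value t(1 − alpha/2, n − 1).

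**Step 1: reproduce the plan's figure.** With n = 18 and d = 0.7, the noncentrality is 0.7 × √18 = 2.970. At alpha 0.05 the critical value on 17 degrees of freedom is 2.110, and power is 79.9%. This matches the stated 80% to rounding. Strictly, 19 is the first whole number that reaches 80% (82.3%). The sum is therefore sound on its own inputs.

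**Step 2: use the threshold the SAP applies.** Only the critical value changes for n = 18.

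| n | alpha | Critical t | Noncentrality | Power per metric |
|---|---|---|---|---|
| 18 | 0.05 | 2.110 | 2.970 | 79.9% |
| 18 | 0.0125 | 2.793 | 2.970 | 57.9% |
| 20 | 0.0125 | 2.759 | 3.130 | 64.6% |
| 25 | 0.0125 | 2.700 | 3.500 | 78.0% |
| 26 | 0.0125 | 2.692 | 3.569 | 80.1% |

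The chance of missing a true effect of 0.7 on one metric is 100% − 57.9% = 42.1% with 18 participants, against the implied 20%.

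**Step 3: detectable effect.** At 0.0125, the effect with 80% power is 0.868 for n = 18 and 0.815 for n = 20.

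**Step 4: sensitivity to the effect size, at 0.0125, two-sided.**

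| d | n = 18 | n = 20 |
|---|---|---|
| 0.5 | 28.5% | 32.9% |
| 0.6 | 42.7% | 48.6% |
| 0.7 | 57.9% | 64.6% |
| 0.8 | 72.0% | 78.3% |
| 0.9 | 83.2% | 88.3% |

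**Step 5: sensitivity to the unstated choices, at n = 18, d = 0.7, alpha 0.0125.**
- One-sided t-test: 69.4%.
- Two-sided Wilcoxon: about 55% (simulated normal data), or 49% at its minimum efficiency relative to the t-test (0.864).
- One-sided Wilcoxon at that minimum efficiency: 61.0%.
- Normal approximation, which overstates power in a sample this small: 68.2% two-sided, 76.7% one-sided.

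None reaches 80%.

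**The case against.** Five points can be made on the other side.

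- **The 58% is conditional.** The SAP states neither sidedness nor the definition of its effect size, and 18 can also be reached at 0.05 by a one-sided Wilcoxon calculation at minimum efficiency. This stands as a caveat. The two-sided reading is the natural one, since the null is no difference and a one-sided t-test at 0.05 would need only 15. The t and Wilcoxon variants run from about 49% to 69%.
- **Per-metric power is not study power.** The SAP has no rule saying whether one significant metric is enough or all four are needed. If all four metrics had d = 0.7, simulation at n = 18 and 0.0125 gives the power for at least one as about 97%, 87% and 77% for correlations of 0, 0.5 and 0.8. For all four together it is about 11%, 25% and 38%. This also stands, but it does not rescue the 80%: the Power Analysis describes a single pairwise comparison, and the documents give no correlations.
- **The wording leaves room for more than eighteen.** It does, but no larger target is set, and the 20 in Table 1 still fall short.
- **The stakes are modest.** The protocol's Statistical Analysis section disclaims statistical significance as an aim, and the SAP will report confidence intervals, which would show imprecision. Type I error is not affected. However, the SAP's opening sentence sets out to test significance, and its power claim should match its own threshold.
- **The citation point rests on a title.** The paper itself is not available here, so it cannot be said where in it the 0.7 arose. What can be said is that the printed title does not concern gait and that the SAP shows no derivation.

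**Conclusion.** The concern holds. The Power Analysis is correct for alpha 0.05, but the SAP makes no comparison at 0.05, so its power statement is inconsistent with its own testing rule. At 0.0125, power per metric is 57.9% with 18 participants and 64.6% with 20, and 26 are needed for 80%. These figures assume a two-sided paired t-test and 0.7 as the standardised paired difference. Other choices move the number, but none restores 80%. The effect size of 0.7 has no gait basis in the documents and should be read as an assumption. If the true effect were 0.5, power would be about 29% to 33%.

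**What to change.** Rewrite the Power Analysis at the threshold the SAP uses, for example:

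> With a two-sided paired t-test at alpha 0.0125 and a standardised paired difference of 0.7, 18 participants give 58% power per metric and 20 give 65%. Power of 80% is available for a difference of about 0.87 with 18 participants or 0.815 with 20.

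Label 0.7 as an assumption, stop citing the reaching-and-grasping paper as support for a gait effect, and add the power table for d from 0.5 to 0.9. State the sidedness and the definition of the effect size in the same paragraph.

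The cost is SAP wording only, and the stated power becomes less favourable. No extra participants are needed.

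If the sponsor wants to keep 80%, two other routes work on the SAP's own inputs. One is to name a single primary metric tested at 0.05 before any data are seen (79.9% with 18). The other is to plan 26 participants, which is 26 − 20 = 6 more than Table 1 foresees for Session C.

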## Reported Outcomes

For each metric of interest, we will take the average of each participant's metric values across steps for both noFES and FES walking. We will also report the 95% confidence interval for the differences between FES and noFES outcome metrics.

## Tests of Statistical Significance

The Shapiro-Wilk test for normality will be used to assess the assumption of normality. If the outcome variable is approximately normally distributed, a paired t-test will be used to statistically compare noFES and FES outcome metrics. If the normality assumption is not met, the Wilcoxon signed rank test will be used as an alternative to the paired t-test for this statistical comparison. Bonferroni multiple hypothesis correction will be utilized (four outcome metrics), and our corrected significance level for comparison is 0.0125 (0.05 divided by the four hypotheses tested).

 N. Kapadia, B. Moineau, and M. R. Popovic, "Functional Electrical Stimulation Therapy for Retraining Reaching and Grasping After Spinal Cord Injury and Stroke," *Front. Neurosci.*, vol. 14, p. 718, Jul. 2020, doi: 10.3389/fnins.2020.00718.

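### Does the rule that chooses between the paired t-test and the Wilcoxon test check normality of the wrong quantity?

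*SAP*

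**What the plan says.** The SAP's opening section describes the analysis as a "pairwise comparison (single sample, pre-test post-test" design. Under Reported Outcomes, "we will take the average of each participant's metric values across steps for both noFES and FES walking", which gives two values per participant for each metric. The same section adds: "We will also report the 95% confidence interval for the differences between FES and noFES outcome metrics".

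Tests of Statistical Significance then gives the rule in three consecutive sentences:

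- First comes the check itself: "The Shapiro-Wilk test for normality will be used to assess the assumption of normality".
- Next is the branch followed when the check is passed: "If the outcome variable is approximately normally distributed, a paired t-test will be used to statistically compare noFES and FES outcome metrics".
- Last is the branch followed when the check fails: "If the normality assumption is not met, the Wilcoxon signed rank test will be used as an alternative to the paired t-test".

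The rule applies to four metrics, each tested at 0.0125. The SAP gives no Shapiro-Wilk cut-off and does not define the singular *outcome variable*. The Statistical Analysis section of the protocol is silent on the point.

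**The concern.** A paired t-test is a one-sample t-test on the within-participant differences, and its normality assumption concerns those differences. Normality of the two sets of averages is neither necessary nor sufficient. Skewed walking speeds can yield normal differences, and normal-looking speeds can hide skewed or heavy-tailed ones.

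The SAP uses *outcome metrics* for the noFES and FES values and mentions differences only for the confidence interval. A literal reader could therefore run Shapiro-Wilk on the averages. The check decides which of two p-values counts for each metric, so two analysts could report different tests on the same data and occasionally disagree about significance.

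**Working it through.** **1. The wording.** The first sentence of the rule speaks of an assumption. The third says what happens when that assumption fails: "the Wilcoxon signed rank test will be used as an alternative to the paired t-test". The assumption is therefore the paired t-test's own, which is about the differences, and the single-sample pairwise framing points the same way. The middle sentence uses an undefined singular. On the literal reading each metric has two variables, noFES and FES, and the phrase does not say which is meant. The wording is ambiguous; it does not clearly name a different quantity.

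**2. The plan's own figures.** Inputs from the SAP: n = 18, effect size 0.7 (taken as mean difference over SD of differences), alpha 0.05 (taken as two-sided). With df = 17 and noncentrality 0.7 × √18 = 2.97, the power of the paired t-test is 79.9%, so 18 reproduces to rounding. The corrected level is 0.05 / 4 = 0.0125. At that level the same formula gives 57.9%, which is the baseline for step 4. The choice of 0.05 for the power analysis is a separate matter. None of these figures depends on which quantity is checked.

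**3. How often the chosen test differs.** Assumed: Shapiro-Wilk cut-off 0.05, n = 18, 5,000 samples per case. The check is made either on the differences or on the two conditions, with non-normality declared if either is flagged.

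| Case | Differences flagged | Either condition flagged | Choice differs |
|---|---|---|---|
| Both normal | 5% | 8% | 12% |
| Skewed levels, normal differences | 5% | 62% | 61% |
| Normal levels, skewed differences | 78% | 8% | 73% |

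**4. How often the decision differs.** Assumed: 30,000 samples per case, noFES SD twice the SD of the differences, effect 0.7, level 0.0125, exact signed-rank p-values. In the last two columns the first figure is for checking either condition and the second for checking the differences.

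| Case | Decision changes | Power | Rejection at zero mean difference |
|---|---|---|---|
| All normal | 0.9% | 57.6 / 57.9% | 1.14 / 1.15% |
| Log-normal levels | 3.4% | 56.4 / 58.0% | 1.33 / 1.42% |
| Differences t, 3 df | 5.7% | 73.4 / 78.5% | 0.84 / 1.12% |
| Exponential differences | 13.3% | 68.5 / 72.9% | 3.97 / 4.80% |

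The 57.9% for normal data agrees with the formula in step 2.

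**5. Taking out the size effect.** In every row, checking the differences also rejects more often when the mean difference is zero, so part of its extra power comes from a larger rejection rate. If its level is lowered until the zero-difference rates match, its power becomes 57.7, 57.3, 75.7 and 68.5%. The remaining advantages are:

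- normal: 57.7 − 57.6 = 0.1 points
- log-normal levels: 57.3 − 56.4 = 0.9 points
- t, 3 df: 75.7 − 73.4 = 2.3 points
- exponential: about 0

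These matched figures are noisy. The Monte Carlo standard error of a rate near 1.25% is √(0.0125 × 0.9875 / 30,000) = 0.06 points, close to the 0.09-point contrast (1.42 − 1.33) used for matching in the log-normal row. A 60,000-sample run gave 1.25% against 1.17% there.

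**6. Range.** SD ratios of 1, 2 and 4 were combined with three literal readings (noFES only, FES only, either). Decisions change in 0.6–0.9% (normal), 1.1–3.5% (log-normal levels), 4.0–7.2% (t, 3 df) and 10–14% (exponential) of samples. At zero mean difference they change in 0.04–0.34%, or 1.3–1.6% with exponential differences. Over four metrics the chance of at least one change is at most four times the single-metric figure: 4 × 0.34 = 1.36% at zero mean difference (exponential case aside), and 4 × 0.9 = 3.6% for normal data at effect 0.7.

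**The case for a change.** The strongest opposing case is that a pre-specified rule deciding which p-value counts should not rest on inference. The SAP's own vocabulary treats a difference as something taken between outcome metrics, so *outcome variable* leans towards the averages. The reported test could differ in 61% or 73% of data sets in the skewed cases, the rule runs four times, unmatched power falls by 5.1 points with t (3 df) differences, and a single clause would settle it.

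Part of this stands. No sentence names the differences, and the test reported can depend on the reading. But a different choice of test seldom becomes a different conclusion, because both tests use the same differences and usually agree. The large figures need heavy-tailed or exponential differences, and the documents give no distribution or SD to suggest either. The 5.1-point loss falls to 2.3 once rejection rates are matched. The exponential case does not favour the textbook reading: both readings reject well above 1.25% at zero mean difference (3.97% and 4.80%), since the signed rank test does not test the mean when differences are skewed. Naming the differences would not remove that.

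**Conclusion.** This is a gap in wording that an analyst would fill sensibly, and the plan need not change. The assumption of a paired test in a single-sample design points to the differences. A literal reading still leads to one of two pre-specified paired tests on those same differences, with no higher rejection rate at zero mean difference in any case examined. For normal data the decision changes in under 1% of samples, with a size-matched power difference of about 0.1 points. Under assumed t (3 df) differences these become 4.0–7.2% of samples across the settings and about 2 points (SD ratio 2, either condition flagged).

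The sizes rest on n = 18, effect 0.7 and level 0.0125 from the SAP, and on an assumed 0.05 cut-off, assumed distributions and assumed SD ratios of 1 to 4. The conclusion would be weaker only if the differences were known to be strongly non-normal, which nothing in either document indicates. The protocol's Statistical Analysis section also disclaims any use of the results for clinical diagnosis or recommendation, which limits what an occasional changed decision could affect.
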